6.3.4 Duration of Response

Duration of overall response: The duration of overall response is measured from the time measurement criteria are met for CR or PR (whichever is first recorded) until the first date that recurrent or progressive disease is objectively documented (taking as reference for progressive disease the smallest measurements recorded since the treatment started).

Duration of overall CR: The duration of overall CR is measured from the time measurement criteria are first met for CR until the first date that progressive disease is objectively documented.

Duration of overall non-CR/non-PD: Non-CR/non-PD disease is measured from the start of the treatment until the criteria for progression are met, taking as reference the smallest measurements recorded since the treatment started, including the baseline measurements.

6.4 TOXICITY CRITERIA

Careful evaluation to ascertain the toxicity, immunologic effects and anti-HSIL efficacy of the treatment regimens will be performed. This study will utilize the CTCAE version 5.0 for toxicity and adverse event reporting. A copy of the CTCAE version 5.0 can be downloaded from the website http://ctep.cancer.gov. All appropriate treatment areas should have access to a copy of the CTCAE version 5.0. A copy of the CTCAE version 5.0 can be downloaded from the CTCAE version 5.0. A copy of the CTCAE version 5.0 can be downloaded from the CTCAE version 5.0. A copy of the CTCAE version 5.0 can be downloaded from the CTEP web site (http://ctep.cancer.gov/protocolDevelopment/electronic_applications/ctc.htm).

7 NIH REPORTING REQUIREMENTS/DATA AND SAFETY MONITORING PLAN

7.1 **DEFINITIONS**

Please refer to definitions provided in Policy 801: Reporting Research Events found here.

7.2 OHSRP OFFICE OF COMPLAINCE AND TRAINING / IRB REPORTING

7.2.1 Expedited Reporting

Please refer to the reporting requirements in Policy 801: Reporting Research Events and Policy 802 Non-Compliance Human Subjects Research found here. Note: Only IND Safety Reports that meet the definition of an unanticipated problem will need to be reported per these policies.

7.2.2 IRB Requirements for PI Reporting at Continuing Review

Please refer to the reporting requirements in Policy 801: Reporting Research Events found here.

7.3 NCI CLINICAL DIRECTOR REPORTING

Problems expeditiously reported to the OHSRP in iRIS will also be reported to the NCI Clinical Director. A separate submission is not necessary as reports in iRIS will be available to the Clinical Director.

In addition to those reports, all deaths that occur within 30 days after receiving a research intervention **s**hould be reported via email to the Clinical Director unless they are due to progressive disease.

To report these deaths, please send an email describing the circumstances of the death to [name] at [contact] within one business day of learning of the death.

7.4 INSTITUTIONAL BIOSAFETY COMMITTEE (IBC) REPORTING CRITERIA

7.4.1 Serious Adverse Event Reports to IBC

The Principal Investigator (or delegate) will notify IBC of any unexpected fatal or lifethreatening experience associated with the use of E7TCR transduced PBL cells as soon as possible but in no event later than 7 calendar days of initial receipt of the information. Serious adverse events that are unexpected and associated with the use of the E7 TCR transduced PBL, but are not fatal or life-threatening, much be reported to the NIH IBC as soon as possible, but not

later than 15 calendar days after the investigator's initial receipt of the information. Adverse events may be reported by using the FDA Form 3500a.

7.4.2 Annual Reports to IBC

Within 60 days after the one-year anniversary of the date on which the i IBC approved the initial protocol, and after each subsequent anniversary until the trial is completed, the Principal Investigator (or delegate) shall submit the information described below. Alternatively, the IRB continuing review report can be sent to the IBC in lieu of a separate report. Please include the IBC protocol number on the report.

7.4.2.1 Clinical Trial Information

A brief summary of the status of the trial in progress or completed during the previous year. The summary is required to include the following information:

- the title and purpose of the trial
- clinical site
- the Principal Investigator
- clinical protocol identifiers;
- participant population (such as disease indication and general age group, e.g., adult or pediatric);
- the total number of participants planned for inclusion in the trial; the number entered into the trial to date whose participation in the trial was completed; and the number who dropped out of the trial with a brief description of the reasons
- the status of the trial, e.g., open to accrual of subjects, closed but data collection ongoing, or fully completed,
- if the trial has been completed, a brief description of any study results.

7.4.2.2 Progress Report and Data Analysis

Information obtained during the previous year's clinical and non-clinical investigations, including:

- a narrative or tabular summary showing the most frequent and most serious adverse experiences by body system
- a summary of all serious adverse events submitted during the past year
- a summary of serious adverse events that were expected or considered to have causes not associated with the use of the gene transfer product such as disease progression or concurrent medications
- if any deaths have occurred, the number of participants who died during participation in the investigation and causes of death
- a brief description of any information obtained that is pertinent to an understanding of the gene transfer product's actions, including, for example, information about dose-response, information from controlled trials, and information about bioavailability.

7.5 NIH REQUIRED DATA AND SAFETY MONITORING PLAN

7.5.1 Principal Investigator/Research Team

The clinical research team will meet on a weekly basis when patients are being actively treated on the trial to discuss each patient.

All data will be collected in a timely manner and reviewed by the principal investigator or a lead associate investigator. Events meeting requirements for expediated reporting as described in section 7.2.1 will be submitted within the appropriate timelines.

The principal investigator will review adverse event and response data on each patient to ensure safety and data accuracy. The principal investigator will personally conduct or supervise the investigation and provide appropriate delegation of responsibilities to other members of the research staff.

7.5.2 Safety Monitoring Committee (SMC)

This protocol will require oversight from the Safety Monitoring Committee (SMC). Initial review will occur as soon as possible after the annual NIH Intramural IRB continuing review date. Subsequently, each protocol will be reviewed as close to annually as the quarterly meeting schedule permits or more frequently as may be required by the SMC. For initial and subsequent reviews, protocols will not be reviewed if there is no accrual within the review period. Written outcome letters will be generated in response to the monitoring activities and submitted to the Principal investigator and Clinical Director or Deputy Clinical Director, CCR, NCI.

8 SPONSOR SAFETY REPORTING

8.1 **DEFINITIONS**

8.1.1 Adverse Event

Any untoward medical occurrence in a patient or clinical investigation subject administered a pharmaceutical product and which does not necessarily have a causal relationship with this treatment. An adverse event (AE) can therefore be any unfavorable and unintended sign (including an abnormal laboratory finding), symptom, or disease temporally associated with the use of a medicinal (investigational) product, whether or not related to the medicinal (investigational) product (ICH E6 (R2))

8.1.2 Serious Adverse Event (SAE)

An adverse event or suspected adverse reaction is considered serious if in the view of the investigator or the sponsor, it results in any of the following:

- Death,
- A life-threatening adverse event (see section 8.1.3)
- Inpatient hospitalization or prolongation of existing hospitalization
 - A hospitalization/admission that is pre-planned (i.e., elective or scheduled surgery arranged prior to the start of the study), a planned hospitalization for pre-existing condition, or a procedure required by the protocol, without a serious deterioration in health, is not considered a serious adverse event.

- A hospitalization/admission that is solely driven by non-medical reasons (e.g., hospitalization for patient convenience) is not considered a serious adverse event.
- Emergency room visits or stays in observation units that do not result in admission to the hospital would not be considered a serious adverse event. The reason for seeking medical care should be evaluated for meeting one of the other serious criteria.
- Persistent or significant incapacity or substantial disruption of the ability to conduct normal life functions
- A congenital anomaly/birth defect.
- Important medical events that may not result in death, be life-threatening, or require hospitalization may be considered a serious adverse drug experience when, based upon appropriate medical judgment, they may jeopardize the patient or subject and may require medical or surgical intervention to prevent one of the outcomes listed in this definition.

8.1.3 Life-threatening

An adverse event or suspected adverse reaction is considered "life-threatening" if, in the view of either the investigator or sponsor, its occurrence places the patient or subject at immediate risk of death. It does not include an adverse event or suspected adverse reaction that, had it occurred in a more severe form, might have caused death. (21CFR312.32)

8.1.4 Severity

The severity of each Adverse Event will be assessed utilizing the CTCAE version 5.0.

8.1.5 Relationship to Study Product

All AEs will have their relationship to study product assessed using the terms: related or not related.

- Related There is a reasonable possibility that the study product caused the adverse event. Reasonable possibility means that there is evidence to suggest a causal relationship between the study product and the adverse event.
- Not Related There is not a reasonable possibility that the administration of the study product caused the event.

8.2 Assessment of Safety Events

AE information collected will include event description, date of onset, assessment of severity and relationship to study product and alternate etiology (if not related to study product), date of resolution of the event, seriousness and outcome. The assessment of severity and relationship to the study product will be done only by those with the training and authority to make a diagnosis and listed on the Form FDA 1572 as the site principal investigator or sub-investigator. AEs occurring during the collection and reporting period will be documented appropriately regardless of relationship. AEs will be followed through resolution.

SAEs will be:

• Assessed for severity and relationship to study product and alternate etiology (if not related to study product) by a licensed study physician listed on the Form FDA 1572 as

the site principal investigator or sub-investigator.

- Recorded on the appropriate SAE report form, the medical record and captured in the clinical database.
- Followed through resolution by a licensed study physician listed on the Form FDA 1572 as the site principal investigator or sub-investigator.

For timeframe of recording adverse events, please refer to section **6.1**. All serious adverse events recorded from the time of first investigational product administration must be reported to the sponsor.

8.3 **Reporting of Serious Adverse Events**

Any AE that meets protocol-defined serious criteria or meets the definition of Adverse Event of Special Interest that require expedited reporting must be submitted immediately (within 24 hours of awareness) to OSRO Safety using the CCR SAE report form.

All SAE reporting must include the elements described in section 8.2.

SAE reports will be submitted to the Center for Cancer Research (CCR) at: [contact] and to the CCR PI and study coordinator. CCR SAE report form and instructions can be found at:

https://ccrod.cancer.gov/confluence/pages/viewpage.action?pageId=157942842

Following the assessment of the SAE by OSRO, other supporting documentation of the event may be requested by the OSRO Safety and should be provided as soon as possible.

8.4 SAFETY REPORTING CRITERIA TO THE PHARMACEUTICAL COLLABORATORS

Reporting will be per the collaborative agreement with Kite Pharma (CRADA #03022).

8.5 **REPORTING PREGNANCY**

8.5.1 Maternal exposure

If a patient becomes pregnant during the course of the study, the study treatment should be discontinued immediately, and the pregnancy reported to the Sponsor no later than 24 hours of when the Investigator becomes aware of it. The Investigator should notify the Sponsor no later than 24 hours of when the outcome of the Pregnancy become known,

Pregnancy itself is not regarded as an SAE. However, congenital abnormalities or birth defects and spontaneous miscarriages that meet serious criteria (section $\underline{8.1.2}$) should be reported as SAEs.

The outcome of all pregnancies (spontaneous miscarriage, elective termination, ectopic pregnancy, normal birth, or congenital abnormality) should be followed up and documented.

8.6 REGULATORY REPORTING FOR STUDIES CONDUCTED UNDER CCR-SPONSORED IND

Following notification from the investigator, CCR, the IND sponsor, will report any suspected adverse reaction that is both serious and unexpected in expedited manner to the FDA in accordance to 21 CFR 312.32. CCR will report an AE as a suspected adverse reaction only if there is evidence to suggest a causal relationship between the study product and the adverse event. CCR will notify FDA and all participating investigators (i.e., all investigators to whom the sponsor is providing drug under its INDs or under any investigator's IND) in an IND safety

report of potential serious risks from clinical trials or any other source, as soon as possible, in accordance to 21 CFR Part 312.32.

All serious events will be reported to the FDA at least annually in a summary format.

9 CLINICAL MONITORING

As a sponsor for clinical trials, FDA regulations require the CCR to maintain a monitoring program. The CCR's program allows for confirmation of: study data, specifically data that could affect the interpretation of primary and secondary study endpoints; adherence to the protocol, regulations, ICH E6, and SOPs; and human subjects protection. This is done through independent verification of study data with source documentation focusing on:

- Informed consent process
- Eligibility confirmation
- Drug administration and accountability
- Adverse events monitoring
- Response assessment.

The monitoring program also extends to multi-site research when the CCR is the coordinating center.

This trial will be monitored by personnel employed by a CCR contractor. Monitors are qualified by training and experience to monitor the progress of clinical trials. Personnel monitoring this study will not be affiliated in any way with the trial conduct.

10 STATISTICAL CONSIDERATIONS

10.1 STATISTICAL HYPOTHESES

10.1.1 Primary Efficacy endpoints

The primary efficacy endpoint of this trial is to determine the complete response rate for E7 TCR T cells in the treatment of patients with vulvar HSIL.

10.1.2 Secondary Efficacy endpoint

The secondary objective of this trial is to characterize the safety profile of E7 TCR T cells administered in a low intensity setting without conditioning or systemic aldesleukin.

10.1.3 Sample Size Determination

This trial will be conducted using a Simon minimax two-stage phase II trial design(25) to rule out an unacceptably low CR rate of 5% (p0=0.05) in favor of an improved complete response rate of 25% (p1=0.25). With alpha=0.10 (probability of accepting a poor treatment=0.10) and beta = 0.20 (probability of rejecting a good treatment=0.20), the first stage will enroll 12 evaluable patients, and if 0 of the 12 have a complete response, then no further patients will be accrued. If 1 or more of the first 12 patients have a complete response, then accrual would continue until a total of 16 evaluable patients have been treated. As it may take up to several months to determine if a patient has experienced a complete response, a temporary pause in the accrual may be necessary to ensure that enrollment to the second stage is warranted. If there are 1-2 patients with a complete response out of 16 patients, this would be an uninterestingly low

complete response rate. If there were 3 or more of 16 (18.75%) who experienced a complete response, this would be sufficiently interesting to warrant further study in later trials. Under the null hypothesis (5% complete response rate), the probability of early termination is 54.0%. In patients that undergo retreatment, only the first response to E7 TCR T cell treatment will be used in the calculation of complete response rate.

Since patients will be screened on this protocol, to allow for patients who enroll but are not evaluable for the primary endpoint, as well as screen failures, up to 200 patients total may be enrolled. It is expected that up to 10-12 treated patients can be enrolled within one year; thus, up to 18 months may be required to accrue 16 evaluable patients. Up to 16 patients may be treated in order to allow for a small number of inevaluable, treated patients.

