10.2.2 Analysis of the Primary Endpoints

The fraction of patients who experience a complete response will be reported along with 80% and 95% two-sided confidence intervals.

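### Does the stated alpha of 0.10 misstate the false-positive risk of the 12/16 design, and should the planned confidence intervals change to match?

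*Combined protocol and SAP*

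**What the plan says.** Section 10.1.3 (Sample Size Determination) describes a "Simon minimax two-stage phase II trial design(25) to rule out an unacceptably low CR rate of 5% (p0=0.05"). The alternative hypothesis is a complete response rate of 25%. The false-positive limit is given as "With alpha=0.10 (probability of accepting a poor treatment=0.10"). For the false-negative side, the section puts "beta = 0.20 (probability of rejecting a good treatment=0.20").

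The rule is then spelled out. In stage 1, "the first stage will enroll 12 evaluable patients, and if 0 of the 12 have a complete response, then no further patients will be accrued". With at least one response, "then accrual would continue until a total of 16 evaluable patients have been treated". At the end, "If there were 3 or more of 16 (18.75%) who experienced a complete response, this would be sufficiently interesting". The section also states a 54.0% probability of early termination under the null rate. It reports no attained type I error and no attained power.

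Section 10.2.2 (Analysis of the Primary Endpoints) says that the complete response fraction "will be reported along with 80% and 95% two-sided confidence intervals". It names no interval method and does not link either interval to the decision, which rests on the count in section 10.1.3.

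**The concern.** The gloss on alpha uses an equals sign and plain words, so a reader may take 0.10 as the chance that this particular rule passes a poor treatment. The figures around it encourage that reading: the 54.0% early-termination probability is exact, and beta of 0.20 is almost exact. The actual probability is 0.043, so the stated figure is 0.10 / 0.0427 = 2.3 times too high. The same design would also satisfy alpha of 0.05, so the plan appears to claim weaker evidence than it delivers.

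The intervals seem to add to this. By nominal level, the 80% interval leaves 10% in each tail and the 95% interval leaves 2.5%; neither is 4.3%. At the smallest positive result, 3 of 16, the report could declare success next to a 95% interval that still contains 5%. If that were a real mismatch, a borderline positive trial would be hard to interpret, and it would be unclear which interval bears on the decision to go on to later trials.

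**Working it through.** **Inputs.** All are from section 10.1.3: p0 = 0.05, p1 = 0.25, alpha 0.10, beta 0.20, n1 = 12, stop at 0 responses, n = 16, success at 3 or more. The interval levels of 80% and 95% are from section 10.2.2.

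**1. The plan's own early-termination figure.** P(0 of 12 at 5%) = 0.95^12 = 0.5404. This reproduces the stated 54.0%.

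**2. Attained type I error.** Let X1 be the responses among the first 12 and X2 those among the last 4. Success requires X1 ≥ 1 and X1 + X2 ≥ 3. At p = 0.05:

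| Route | Probability |
|---|---|
| X1 = 1, X2 ≥ 2 | 0.3413 × 0.0140 = 0.0048 |
| X1 = 2, X2 ≥ 1 | 0.0988 × 0.1855 = 0.0183 |
| X1 ≥ 3 | 0.0196 |
| Total | 0.0427 |

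**3. Attained power.** The same sum at p = 0.25 is 0.1267 × 0.2617 + 0.2323 × 0.6836 + 0.6093 = 0.0332 + 0.1588 + 0.6093 = 0.8013. Attained beta is 1 − 0.8013 = 0.1987.

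**4. Is this the right design for the stated limits?** An exhaustive search over two-stage designs, with type I error at most 0.10 and power at least 0.80, finds none with fewer than 16 patients. Among those with 16, stopping at 0 of 12 and failing at 2 or fewer of 16 has the smallest expected sample size under p0: 12 + (1 − 0.5404) × 4 = 13.84. That is the protocol's design. Lowering the type I limit to 0.05 returns the same design.

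**5. Why the attained value is not nearer 0.10.** Keep the sample sizes and the stage 1 rule, and lower the final cut to 2 of 16. The type I error becomes P(X1 = 1) × P(X2 ≥ 1) + P(X1 ≥ 2) = 0.3413 × 0.1855 + 0.1184 = 0.182. So the available values step from 0.182 to 0.043, and a cut of 3 is the lowest that respects 0.10.

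**6. Do the intervals agree with the rule?** Exact (Clopper-Pearson) lower limits for x of 16, treating the result as a plain binomial:

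| x | 80% | 90% | 95% |
|---|---|---|---|
| 2 | 3.4% | 2.3% | 1.6% |
| 3 | 7.1% | 5.3% | 4.0% |
| 4 | 11.4% | 9.0% | 7.3% |

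The 80% interval includes 5% at 2 responses and excludes it at 3, exactly where the rule turns. The 90% interval does the same. The 95% interval needs 4 responses. In general, a Clopper-Pearson lower limit excludes 5% when the upper-tail probability at 5% is below half the non-coverage. Ignoring the interim look, that tail is 0.189 at 2 of 16 and 0.043 at 3 of 16. Agreement with the rule therefore holds for levels from about 1 − 2 × 0.189 = 62% to 1 − 2 × 0.043 = 91%.

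**7. Dependence on the interval method.** With Wilson limits, the 80% lower limit at 2/16 is 5.3%, which excludes 5% although the rule fails. The 95% lower limit at 3/16 is 6.6%, which excludes it. The match in step 6 thus rests on exact limits.

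**The case for a change.** The strongest case for acting is that the text gives a probability which, read as written, is wrong, and that putting it right costs one line. A funder or investigator who takes 0.10 at face value will undervalue a positive result that bears on whether to go further. Section 10.2.2 does not say which interval belongs with the decision or how it is computed, and the method matters, as the Wilson figures show. A 90% exact interval would pair with a one-sided 0.05 and follow the rule on both sides of the cut.

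Part of this stands. The gloss is loose, and an author could usefully write that alpha is at most 0.10, attained 0.043, with power 0.801. Naming the interval method would be tidy. The rest does not carry:

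- Beta of 0.20 is also a ceiling, attained at 0.199. Accepting it as a limit while reading alpha as an exact value is inconsistent.
- The 80% interval is the natural partner of a one-sided 0.10, and its exact version already gives the same answer as the rule. A 90% interval has 5% in each tail, so it does not equal 4.3% either; the level that would is 1 − 2 × 0.0427 = 91.5%. Preferring 90% to 80% is a matter of taste.
- A 95% interval that contains 5% at 3 of 16 is what a stricter level should show. It contradicts nothing, since the decision is made on the count. Keeping the 95% interval beside a 90% one would leave that display in place.

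**Conclusion.** No change to the plan is called for. The nominal alpha of 0.10 is the limit from which the design was found, the design is the correct minimax solution for that limit, and the stated early-termination probability is right. The attained error of 0.043 against 0.10 reflects discreteness and errs on the cautious side: the true false-positive risk is lower than the text suggests. Rewording it would alter neither the sample size nor the cut-offs, the decision or the reported response rate.

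The interval point is likewise not a defect. The planned 80% interval agrees with the 3-of-16 rule when exact limits are used, a conventional choice for a proportion at this sample size and one an analyst can make without an amendment. An unnamed interval method is a gap in detail that the analysis can fill sensibly.

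These conclusions assume exactly 12 and then 16 evaluable patients, as section 10.1.3 states. They also treat the final count as a simple binomial for the intervals; the interim look barely matters for the error rate, which is 0.0427 with it and 0.0429 without.

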3 STUDY IMPLEMENTATION

3.1 STUDY DESIGN

This is a single arm phase II clinical trial using a Simon minimax two-stage design. Twelve patients will be treated initially, which will be expanded to sixteen patients if one or more patient(s) have a complete response in the initial 12 patients.

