3.6.2 Off-Study Criteria

- Screen failure
- Completed study follow-up period

- Inability to generate a cell product. A second attempt may be made to generate a cell product from the patient. If the second attempt fails, that patient will be removed from the study and replaced with another patient.
- Participant requests to be withdrawn from study
- There is significant noncompliance
- The investigators decide to end the study
- The investigators decide it is in the patient's best interest
- Death

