10.1.4 Populations for Analyses

Toxicity Analysis: All patients will be evaluable for toxicity from the time of E7 TCR T cell infusion. Toxicity data will be collected for all patients.

Response Analysis - Intention to treat: any subjects who enroll onto the trial and provide consent and who receive at least one cycle of treatment will be included in analyses.

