10.2.6 Planned Interim Analyses

As indicated in the two-stage design, the number of complete responses noted after 12 evaluable patients have been treated will be noted and will be used to determine if enrollment to the second stage of accrual may proceed.

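### Section 10.1.3 needs 16 evaluable patients but caps treated patients at 16, so its stated allowance for inevaluable treated patients is zero once stage 2 opens

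*Combined protocol and SAP*

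**What the plan says.** Section 10.1.3 describes a Simon minimax design with 12 evaluable patients in stage 1. If at least one has a CR, "accrual would continue until a total of 16 evaluable patients have been treated". Three or more CRs among 16 count as success.

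The same section then sets two ceilings:

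- Enrolment, where the limit leaves room for two groups: "patients who enroll but are not evaluable for the primary endpoint, as well as screen failures, up to 200 patients total may be enrolled".
- Treatment: "Up to 16 patients may be treated in order to allow for a small number of inevaluable, treated patients".

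The document does not use one counting unit throughout:

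- Section 10.2.6 bases the interim decision on "the number of complete responses noted after 12 evaluable patients have been treated".
- Section 3.1 has no such qualifier: "Twelve patients will be treated initially, which will be expanded to sixteen patients". The Précis also gives 12 and 16 without it.
- Section 10.1.4 defines the response population, under an intention-to-treat label, as "any subjects who enroll onto the trial and provide consent and who receive at least one cycle of treatment will be included in analyses".
- Section 10.2.2 sets the estimate: "The fraction of patients who experience a complete response will be reported along with 80% and 95% two-sided confidence intervals".

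The only explicit replacement rule, in section 3.6.2, concerns failure to make a cell product: "If the second attempt fails, that patient will be removed from the study and replaced with another patient".

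**The concern.** A ceiling on treated patients leaves room for inevaluable ones only if it exceeds the number of evaluable patients required. Here the two numbers are equal. If one treated patient turns out inevaluable after stage 2 opens, the evaluable target cannot be met within the ceiling. The team would then have to exceed the ceiling, decide on 15 patients with no stated rule, or count the patient as a non-CR. It would make that choice in an open single-arm trial with responses already known.

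The interim look has a related problem. Whether an unassessed patient counts toward the 12 can determine whether the stopping condition of no CR in 12 has been reached.

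The effect on power depends on something the plan leaves open: whether the 25% target describes all treated patients or only those whose response can be assessed.

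**Working it through.** **Inputs (section 10.1.3).** p0 = 0.05, p1 = 0.25, alpha = 0.10, beta = 0.20. Stage 1 has 12 patients and stops at 0 CR. The total is 16, with success at 3 or more CRs. The stated probability of early termination at 5% is 54.0%. The ceiling is 16 treated.

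**1. The plan's own figures.** With X ~ Bin(12, p) in stage 1 and Y ~ Bin(4, p) in stage 2:

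P(success) = P(X ≥ 3) + P(X = 2)·P(Y ≥ 1) + P(X = 1)·P(Y ≥ 2)

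- Early termination at 5%: 0.95^12 = 0.5404, which matches 54.0%.
- Power at 25%: 0.6093 + 0.2323 × 0.6836 + 0.1267 × 0.2617 = 0.8013.
- Type I error at 5%: 0.0196 + 0.0988 × 0.1855 + 0.3413 × 0.0140 = 0.0427.

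The design is correct as a design, but power exceeds its 80% target by only 0.1 percentage point.

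**2. The allowance.** Treated ceiling minus evaluable patients required:

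- Stage 2 opens: 16 − 16 = 0.
- Trial stops after stage 1: 16 − 12 = 4.

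The probability of reaching stage 2 is 1 − (1 − p)^12. This is 1 − 0.0317 = 96.8% at 25%, and 1 − 0.5404 = 46.0% at 5%.

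**3. Other possible sources of a treated place.** The 200-patient limit applies to enrolment and adds no infusion. The replacement rule in section 3.6.2 covers patients for whom no product could be made, who are never infused. The Précis and section 3.1 both give 16.

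**4. Power if 25% is the rate among assessable patients.** The ceiling stays at 16 and 3 CRs are still required. Where the interim look waits for 12 evaluable patients, the loss reduces stage 2 (12+3, 12+2). Where the lost patient occupies a stage 1 place, it reduces stage 1.

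| Inevaluable | Assessable, stage 1 + stage 2 | Power at 25% | Type I error at 5% |
|---|---|---|---|
| 0 | 12+4 | 80.1% | 0.043 |
| 1 | 12+3 or 11+4 | 76.3% or 76.2% | 0.036 |
| 2 | 12+2, 11+3 or 10+4 | 71.9%, 71.8% or 71.6% | 0.030 |

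Worked case, 12+3: 0.6093 + 0.2323 × 0.5781 + 0.1267 × 0.1563 = 0.7634.

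**5. Power if 25% is the rate among all treated patients.** All 16 count and an unassessed patient is a non-CR already included in the 25%. Power is 80.1% whatever the number unassessed.

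**6. How likely a loss is.** The documents give no inevaluable rate, so the rates here are assumptions. The chance of at least one among 16 is 1 − (1 − d)^16:

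- d = 2%: 28%
- d = 5%: 56%
- d = 10%: 81%

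**The case against.** The strongest reply is that section 10.1.4 already supplies the rule. Everyone infused is analysed, so 16 infused means 16 counted, and a patient without a documented CR stays in the denominator. If the 25% describes that population, power is unaffected. This is a fair reading, and the plan is not silent. It does not reconcile the text, however. Sections 10.1.3 and 10.2.6 still count evaluable patients, and on this reading that word and the allowance sentence have no function.

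A second reply is that two of the three choices lead to the same decision. Deciding on 15 patients and counting the lost patient as a non-CR both need 3 CRs, because a threshold of 2 with 15 patients has a type I error of about 0.167 (12+3) or 0.163 (11+4), above the planned 0.10. That stands for the final go/no-go decision. It does not settle the reported fraction (3/15 = 20% against 3/16 = 18.75%), its confidence intervals, or whether the ceiling may be exceeded.

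A third reply is that losses may be rare. Section 6.3.3.3 uses the best response recorded from the start of treatment and section 3.3 schedules visits at 1, 2 and 3 months, so one missed visit need not make a patient inevaluable. This also stands, and the assumed loss rates should carry little weight. But section 10.1.3 itself expects a small number of such patients.

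**Conclusion.** The concern holds. On the stage 2 path the stated allowance is exactly zero, and no other provision supplies one. This is an internal inconsistency in the rule for the primary denominator. The design parameters all reproduce, and type I error does not rise under either reading.

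The cost in power is conditional. If the 25% refers to assessable patients, the planned beta of 0.20 is missed with the first inevaluable patient (a loss of about 4 percentage points) and by more with a second (about 8 points). If it refers to all treated patients, nothing is lost. The contradiction itself needs no assumption. The power loss rests on the assessable-only reading, and the chance that a loss occurs rests on a rate the documents do not give. It should be fixed, but it does not invalidate the trial.

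**What to change.** **Main change.**

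- Delete the allowance sentence from section 10.1.3.
- In sections 10.1.3 and 10.2.6, drop the evaluable qualifier so that both decision points (12 and 16) count all infused patients, first course only, in line with section 10.1.4.
- State that a patient with no documented CR counts as a non-CR.
- State which population the 25% describes: all infused patients (power 80.1%), or assessable patients (about 76% with one unassessed and about 72% with two).

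This is a wording amendment to two sections and needs no extra patients. The stated power may become slightly less favourable.

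**If the sponsor wants a real allowance.** The treated ceiling must exceed 16 and the assumed loss d must be stated. Keep the threshold of 3 CRs and stage 1 at 12 infused, count unassessed patients as non-CR, and use an effective rate of 0.25 × (1 − d):

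| Infused | Assumed loss | Power | Type I error at most |
|---|---|---|---|
| 16 | 5% | 76.8% | 0.043 |
| 17 | 5% | 80.2% | 0.050 |
| 16 | 10% | 73.1% | 0.043 |
| 18 | 10% | 79.9% | 0.057 |
| 19 | 10% | 82.6% | 0.065 |

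All stay within the planned alpha of 0.10. The cost is one more infused patient at an assumed 5% loss and three more at 10%. Simple inflation at 10%, 16/0.90 = 17.8, rounds up to 18, which falls just short of 80% power.
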